3.4.2.3. Supplementary analyses

- To meet the secondary objective, the Minimal Effective Dose (MED) will be estimated using the selected model resulting from the primary analysis.

The MED is defined as:

$$MED = \min(d: f(d) > f(d_0) + \Delta, L(d) > f(d_0))$$

with Δ is the clinically relevant difference, $L(d)$ the lower confidence limit of the predicted mean value $f(d)$ at dose d.

The estimator will be provided considering a hypothesis of a clinically relevant effect as compared to placebo of 6.5%. A confidence interval will be provided by bootstrap method.

- The primary analysis will be repeated in the PPS.
- For RU area, description at each visit and the relative change from baseline to each visit will also be provided in FAS and PPS.
- Description of the relative change from W006 to W008 of the reference ulcer (RU) area, for patients with a non null value at W006, as well as the description of the relative change from W004 to W006, for patients with a non null value at W004, will be described in FAS and PPS.

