The participants will enter a 6-week ambulatory IMP treatment period on top of standard of care (standardized compression and local wound care with sterile saline solution or sterile water and “non-active” dressing) followed by a 2-weeks follow-up period with standard of care only. During this period the participants will return to the investigator’s site for intermediate visits after one week (W001), two weeks (W002), three weeks (W003), four weeks (W004), six weeks (W006) and eight weeks (W008). Participants will continue to receive standardized compression therapy and local wound care (sterile saline solution or sterile water and “non-active” dressing) until the end of the study (W008). At W000, W004 and W006 visits, pain assessment will be performed at the beginning of the visit using a questionnaire with VAS. At each visit, the clinical features of the RU will be recorded and a 3D picture of the RU will be taken after wound bed preparation. All 3D pictures will be recorded and uploaded for central review, measurement of ulcer area, perimeter and volume for the primary and secondary endpoints of the study.

Four PK samples will be taken at W000, W004 and W006 visits and one predose PK sample will be taken at W001 and W002 visits in all participants. The participants who agreed to participate in the optional PK analysis in participating centres (7 patients per dose group) will have 9 PK samples collected over 12 hours at W000 visit and 13 PK samples collected over 24 hours at the W004 visit instead of the 4 PK samples.

At each visit general compliance with standardized compression will be checked and size of the stockings will be adjusted, if needed. The participant should be explained that the standardized compression stockings should be worn everyday and used according to the recommendations given by the investigator.

- If complete healing of the reference ulcer is observed during the study conduct but other ulcers are still open, the participant will keep the same standardized compression until complete healing of all ulcers is observed or until the end of the study and will continue to take IMP treatment until W006 visit.

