3.4.3. Secondary efficacy criteria

Definition:

- Reference Ulcer Volume (using a digital 3D imaging device).
- Linear advance of the wound margin towards the wound centre.
- Pain intensity (using a questionnaire including a Visual Analog Scale (VAS)).
- Analgesic drug consumption (patient using analgesic drug for Venous Leg Ulcer (VLU) during the study).

Analyses:

For all secondary efficacy criteria, descriptive statistics at each concerned visit will be performed in the FAS and PPS.

The Reference Ulcer volume, will be described at each visit, on the change from baseline to each visit, as well as the description of the change from W004 to W006 and from W006 to W008.

Linear advance of the wound margin towards the wound centre will be described at each visit.

Pain intensity will be described at each concerned visit (W000, W004 and W006) and on the change from baseline to W004 and W006.

Analgesic drug consumption will be described through the question “Need to take medication for control of the pain associated with VLU?” From the pain questionnaire at each concerned visit (W0, W4 and W6).

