5.2.3. Efficacy analysis

Linear advance of the wound margin

Computation of **linear advance** of the wound margin towards the wound center from baseline:

$$\bar{d} = \frac{\Delta A}{\bar{p}}$$

Where ΔA is the difference in the area ($A_{\text{visit}} - A_{\text{baseline}}$) and p the average of the wound perimeter:

$$(\bar{p} = \frac{P_{\text{visit}} + P_{\text{Baseline}}}{2})$$

Computation of **linear advance** of the wound margin towards the wound center from previous visit:

$$\bar{d} = \frac{\Delta A}{\bar{p}}$$

Where ΔA is the difference in the area ($A_{\text{visit } v} - A_{\text{visit } v-1}$) and p the average of the wound perimeter:

$$(\bar{p} = \frac{P_{\text{visit } v} + P_{\text{visit } v-1}}{2})$$

Pain intensity

Pain intensity is defined as the Visual Analog Scale (VAS) values.

In case of response “No” to the question “Does the participant feel any pain or discomfort related to his/her leg ulcer?” and the VAS value is missing this value will be imputed to zero.

Diabetic status

For efficacy analysis, a patient with $\text{HbA1c} \geq 6.5\%$ or a medical history in the following list : 1689.2 Evidences of diabetes mellitus M220 is considered as diabetic.

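### The W004–W006 and W006–W008 relative area changes leave out ulcers already healed at the start of the interval, so arms may not be comparable on them and the off-treatment summary omits re-opening

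*SAP*

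**What the plan says.** SAP 3.4.2.3 plans two interval summaries of reference ulcer area, in the FAS and the PPS:

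- the late on-treatment interval: "relative change from W004 to W006, for patients with a non null value at W004";
- the off-treatment interval: the relative change between W006 and W008, "for patients with a non null value at W006".

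The preceding bullet of the same section has no such restriction: "For RU area, description at each visit and the relative change from baseline to each visit will also be provided in FAS and PPS".

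For volume, SAP 3.4.3 uses the plain change rather than the relative change, over the same two intervals and without excluding healed ulcers: "as well as the description of the change from W004 to W006 and from W006 to W008". SAP 5.2.3 also defines the linear advance "of the wound margin towards the wound center from previous visit".

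Patients whose ulcer heals stay under observation. Protocol 4.2.1 has a rule that begins "If complete healing of the reference ulcer is observed during the study conduct" and keeps the participant on study drug until W006. Protocol 7.1 has the area read centrally at W004, W006 and W008. The form in Protocol Appendix 10 records complete healing and new ulceration. The SAP plans no table of healed or re-opened ulcers.

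**The concern.** Whether the ulcer is still open at W004 or W006 is an outcome observed after randomisation, and one the drug is meant to change. Restricting a summary to open ulcers compares differently selected subsets of the arms whenever healing differs by dose.

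The W006–W008 interval has a further problem. Study drug stops at W006, so this is where loss of healing off treatment would show. The planned percentage admits the favourable transition (open to healed) and leaves out the unfavourable one (healed to open), although the area is measured at both visits. With no healed or re-opened counts, a reader of the report could see neither how many patients each arm lost from the summary nor how many ulcers re-opened.

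**Working it through.** **1. What the restriction removes.** Following the form of the SAP 3.1.2 definition, the relative change over W006–W008 is 100 × (A_W008 − A_W006) / A_W006. It is undefined when A_W006 = 0. I read non-null as non-zero, in line with SAP 5.2.2, which calls the duration null for patients who took no dose.

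| Area at W006 | Area at W008 | Relative change W006–W008 |
|---|---|---|
| open | healed | −100%, included |
| open | open | included |
| healed | healed | excluded |
| healed | open again | excluded |

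The same table holds for W004–W006, but treatment continues through that interval.

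**2. Where re-opening does appear.** Illustration with assumed values: baseline 10 cm², healed at W006, 1 cm² at W008, circular ulcer.

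- Relative change W006–W008: undefined, patient left out.
- Relative change from baseline: 100 × (0 − 10)/10 = −100% at W006 and 100 × (1 − 10)/10 = −90% at W008.
- Linear advance from the previous visit: perimeter at W008 = 2√(π × 1) = 3.545 cm; mean perimeter = (3.545 + 0)/2 = 1.772 cm; advance = (1 − 0)/1.772 = +0.56 cm.
- Volume change W006–W008: positive for any non-zero volume at W008.

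The W008 area, the change from baseline to W008, the volume change and the linear advance from the previous visit therefore all register the event. None identifies it as a re-opening.

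**3. Possible size of the exclusion at W004.** The documents give no healing rate. The nearest inputs are the planning values in Protocol 10.2 and SAP 1.3: SD 42, mean reduction 32.5% on placebo and 62.5% at maximal effect. These values reproduce the plan's own sample size: minimum power over the seven candidate models is 79.9% at 26 per arm and 81.5% at 27; 27/0.8 = 33.75, so 34 per arm, and 34 × 6 = 204.

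Assume that a reduction of 100% or more under that normal model means healed:

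- mean 32.5: 1 − Φ((100 − 32.5)/42) = 1 − Φ(1.607) = 5.4%;
- mean 62.5: 1 − Φ((100 − 62.5)/42) = 1 − Φ(0.893) = 18.6%.

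| Patients per arm | Excluded, placebo | Excluded, maximal effect |
|---|---|---|
| 121/6 = 20.2 (included, if split equally) | 1.1 | 3.8 |
| 34 (planned) | 1.8 | 6.3 |

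**4. Range at W006, with assumed healed shares and 20 per arm.**

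| Healed, placebo / active | Extra patients lost from active arm |
|---|---|
| 5% / 10% | 20 × 0.05 = 1 |
| 10% / 30% | 20 × 0.20 = 4 |
| 20% / 20% | 0 |

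**5. Direction.** Assumed example, 20 per arm. Active: 4 healed at W004 and staying healed, 16 going from 40% to 20% of baseline area. Placebo: 1 healed and staying healed, 19 going from 70% to 50%.

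- SAP metric, open ulcers only: active (20 − 40)/40 = −50%; placebo (50 − 70)/70 = −29%.
- Change in percent of baseline, all patients: active 16 × (−20)/20 = −16 points; placebo 19 × (−20)/20 = −19 points.

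The two metrics rank the arms in opposite order here. Neither is the correct one by itself, and the direction of any distortion cannot be settled in advance.

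**The case against.** The strongest reply is that little is hidden. Unrestricted area and change from baseline are planned at every visit. Volume change covers both intervals, and SAP 5.2.3 defines a linear advance between successive visits. A percent-of-baseline interval change would be the difference of two relative changes already planned, so for patients with both values its mean follows from planned outputs. The outputs criticised are descriptive, and the protocol's area endpoints are all measured against baseline.

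Most of that stands, and it rules out three stronger readings.

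- A reader might infer that re-opening after stopping treatment is never counted, or that these are the only summaries of the late periods. The documents contradict both: re-opening enters the outputs listed in step 2.
- A reader might infer that arms lose patients in proportion to efficacy. The loss follows the healed fraction at the start of the interval, which need not track the mean effect.
- A reader might infer that an effective dose must look worse from W004 to W006. Nothing in the documents shows that, and step 5 gives a case where the open-ulcer metric favours the better arm.

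The reply does not remove the core point. The two interval summaries are still selected on outcome, the W006–W008 one still leaves out re-opening, and means over the whole arm do not say how many ulcers re-opened.

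**Conclusion.** The point holds as a minor one. Both interval relative changes condition on an open ulcer at the start of the interval, and the off-treatment summary leaves out loss of healing by construction. They cannot be compared across doses without knowing how many patients each arm lost, and the SAP does not plan to report that.

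The figures of about 5% versus 19% excluded at W004 are illustrative. They rest on reading the part of a normal distribution beyond 100% reduction, which cannot occur, as the healed share. If healing is equal across arms there is no differential loss. The exclusion itself rests on reading non-null as non-zero. If it meant non-missing, healed ulcers would not be excluded but their percentage would be undefined, and the SAP wording would still need changing.

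The primary MCP-Mod analysis at W004 and the MED keep healed ulcers at 100% reduction. They and the sample size are unaffected.

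**What to change.** In SAP 3.4.2.3:

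1. Keep the two relative changes, label them as conditional on an open ulcer at the start of the interval, and give the number excluded per arm for that reason.
2. Add the plain area change W004–W006 and W006–W008 (A_W006 − A_W004 and A_W008 − A_W006, in cm²) for all FAS patients with both values, as SAP 3.4.3 already does for volume.
3. Tabulate by arm the number healed (area zero) at W004, W006 and W008, and the number healed at W004 or W006 with a non-zero area at a later visit.

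The cost is SAP wording and a few descriptive tables; the data are already collected. The drawback is a ceiling effect: ulcers that stay healed contribute zero to the plain change, which can make an arm with much healing appear to improve less. The plain change must therefore be read alongside the counts in item 3.

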3.4.3. Secondary efficacy criteria

Definition:

- Reference Ulcer Volume (using a digital 3D imaging device).
- Linear advance of the wound margin towards the wound centre.
- Pain intensity (using a questionnaire including a Visual Analog Scale (VAS)).
- Analgesic drug consumption (patient using analgesic drug for Venous Leg Ulcer (VLU) during the study).

Analyses:

For all secondary efficacy criteria, descriptive statistics at each concerned visit will be performed in the FAS and PPS.

The Reference Ulcer volume, will be described at each visit, on the change from baseline to each visit, as well as the description of the change from W004 to W006 and from W006 to W008.

Linear advance of the wound margin towards the wound centre will be described at each visit.

Pain intensity will be described at each concerned visit (W000, W004 and W006) and on the change from baseline to W004 and W006.

Analgesic drug consumption will be described through the question “Need to take medication for control of the pain associated with VLU?” From the pain questionnaire at each concerned visit (W0, W4 and W6).

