4. STUDY DESIGN

4.1. Endpoint(s)

Table (4.1) 1 – Endpoints

Endpoints	
Primary	Relative reduction of Reference Ulcer area after 4 weeks of treatment
Secondary	Relative reduction of Reference Ulcer area after each visit Linear advance of the wound margin towards the wound centre Reference reduction of Reference Ulcer volume at each visit Pain assessment by VAS Analgesic daily dose Safety assessment Adverse event Laboratory parameters Physical examination, body weight, vital signs 6 or 12-leads electrocardiogram
Exploratory	Pharmacokinetics in plasma Genomic in blood Non genomic biomarkers in plasma and serum

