4.1.2. Secondary Endpoints

- Reference Ulcer Area using a digital 3D imaging device: Relative reduction of Reference Ulcer area after each visit on top of standard of care compared with baseline Reference Ulcer area.
- Linear advance of the wound margin towards the wound center ([Gilman, 1990](#)) to measure healing progress at each visit on top of standard of care compared with baseline (see [section 10](#) for more details)
- Reference Ulcer volume using a digital 3D imaging device: relative reduction of Reference Ulcer volume at each visit on top of standard of care compared with baseline Reference Ulcer volume.

- Pain assessment (W000, W004, W006): change in intensity and in the characteristics at each visit compared with baseline (W000), using a questionnaire including a VAS scale
- Analgesic drug consumption (W0, W4, W6): change in daily dose of analgesic taken for VLU at each visit compared with baseline (W000) (patient using analgesic drug for VLU during the study)
- Safety measurements
 - o Adverse events occurring during the double-blind period of the study.
 - o Assessment of laboratory parameters, physical examination, body weight, Vital signs (blood pressure, heart rate), 6 or 12-lead electrocardiogram (ECG).

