The parameters of the selected model in the main analysis will be re-assessed and, if the model converges, it will be used to estimate the MED. If the model doesn’t converge, the second “best” fit model will be used.

- Description

The relative change from baseline of the reference ulcer area will also be described at each visit.

- Secondary criteria

- Linear advance of the wound margin towards the wound centre

Description at each visit will be provided.

- Reference Ulcer Volume

Descriptive statistics at each visit will be performed.

- Pain intensity

Descriptive statistics at each visit will be carried out.

- Analgesic drug consumption

Descriptive statistics at each visit will be carried out.

In addition, relative change of the reference ulcer area, linear advance of the wound margin towards the wound centre and reference ulcer volume will be described at each visit in the following subgroups:

- Combined prognosis criteria on size and age of the ulcer ($\leq 10 \text{ cm}^2$ and ≤ 6 months / $> 10 \text{ cm}^2$ or > 6 months)
- Size of the ulcer at baseline ($\leq 50 \text{ cm}^2$ / $> 50 \text{ cm}^2$)
- Diabetes status (yes/no).

Exploratory data analyses will be conducted as applicable.

Safety

Safety analyses will be carried out on the Safety Set by group over the W0-W6 period.

- Adverse events

Number of adverse events, number and percentage of patients reporting at least one adverse event will be described by System Organ Class (SOC) and Preferred Term. The same analysis will be performed for emergent adverse events and serious adverse events.

Emergent adverse events will be also described in accordance to the intensity, outcome, relationship to the study treatments, and adverse events leading to the study drug withdrawal.

- Clinical laboratory evaluation

Laboratory parameters will be described using value at the visit, last value under treatment and change from baseline to last value under treatment.

Moreover, biochemistry, haematology and urinary parameters will be classified according to the laboratory reference ranges and alert values for the potentially clinically significant abnormal values, and shift tables from baseline to worst event will be presented.

- Physical Examination and vital signs

Physical examination and vital signs will be described using value at the visit, last post-baseline value and change between baseline and last post-baseline value.

- 6 or 12-lead electrocardiogram (ECG)

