3.1.2. General definitions

The following definitions will be considered:

- **IMP** is the treatment intake (S42909 or Placebo) post randomisation.
- **Analysable value** will be defined as any non-missing value.
- **Baseline value** will be defined as the last analysable value prior to the first IMP intake (*i.e.* before or the same date as the first IMP intake date).
Note: In case of patient included and/or randomised but not treated (*i.e.* patients with treatment duration equal to 0): value at baseline is defined as the last analysable value prior or equal to the date of the inclusion visit.
- **Post-baseline value** will be defined as any value recorded at a given timepoint after baseline.
- **Change from baseline** will be defined as the arithmetic difference between a post-baseline value and the baseline value for a given variable at a given time point.
- **Relative change from baseline** will be defined as : $100 * \text{change from baseline} / \text{baseline value}$.

For safety criteria (except for adverse events), the following definitions will be applied:

- A value is considered under treatment if the assessment date is between the first IMP intake date (excluded) over the W000 and W006 period and the last IMP intake date "+ 15 days" (included).

Note: for all definitions concerning value under treatment '+ 15 days' was calculated according to the half-life of the S42909.

- High emergent abnormal value under treatment according to the laboratory reference ranges is defined as value \leq ULN (Upper Limit of Normal laboratory reference range) or missing at baseline and $>$ ULN under treatment.
- Low emergent abnormal value under treatment according to the laboratory reference ranges is defined as value \geq LLN (Lower Limit of Normal laboratory reference range) or missing at baseline and $<$ LLN under treatment.

- High emergent abnormal value under treatment according to the cut-offs for PCSA (Potentially Clinically Significant Abnormal value) values is defined as value \leq ULS (Upper Limit used to define potentially clinically Significant abnormal values) or missing at baseline and $>$ ULS under treatment.
- Low emergent abnormal value under treatment according to the cut-offs for PCSA values is defined as value \geq LLS (Lower Limit used to define potentially clinically Significant abnormal values) or missing at baseline and $<$ LLS under treatment.

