3.4.4. Subgroups analysis

In addition, descriptive statistics at each concerned visit of the reference ulcer area, linear advance of the wound margin towards the wound centre and reference ulcer volume will be performed.

Except for the linear advance of the wound margin towards the wound centre, the relative change from baseline (change for volume) will also be described.

These description will be performed in the FAS in the following subgroups:

- Combined prognosis criteria on size and age of the ulcer ($\leq 10 \text{ cm}^2$ and ≤ 6 months / $> 10 \text{ cm}^2$ or > 6 months) at baseline.
- Size of the ulcer at baseline ($\leq 20 \text{ cm}^2$ / $> 20 \text{ cm}^2$).
- Size of the ulcer at baseline ($\leq 50 \text{ cm}^2$ / $> 50 \text{ cm}^2$).
- Diabetes status (yes/no).

If a subgroup contains less than 20 patients, only listings will be provided for this subgroup.

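### The protocol defines the secondary volume endpoint as relative reduction from baseline, but the SAP plans only raw volume and arithmetic change and does not record the switch

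*SAP*

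**What the plan says.** **Protocol.** Section 4.1.2 defines the volume endpoint as "relative reduction of Reference Ulcer volume at each visit on top of standard of care compared with baseline Reference Ulcer volume", and the synopsis repeats this. The endpoint table in 4.1 reads "Reference reduction of Reference Ulcer volume at each visit", apparently a slip for relative reduction. The statistics section is less specific. Section 10.1.1 lists volume without a scale, and 10.1.4 says of it only "Descriptive statistics at each visit will be performed". The subgroup sentence in 10.1.4, however, opens with the relative scale for a list that ends with volume: "relative change of the reference ulcer area, linear advance of the wound margin towards the wound centre and reference ulcer volume will be described".

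**SAP.** Section 3.1.2 defines two separate quantities. Plain change "will be defined as the arithmetic difference between a post-baseline value and the baseline value for a given variable at a given time point". The relative version is 100 times that change divided by the baseline value. For volume, 3.4.3 states: "The Reference Ulcer volume, will be described at each visit, on the change from baseline to each visit", and adds the changes from W004 to W006 and from W006 to W008. For the subgroups, 3.4.4 states that, apart from linear advance, "the relative change from baseline (change for volume) will also be described".

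**Change record.** The SAP's version table says that it gives the main changes from the analyses planned in the protocol. It has seven entries: linear advance, the 20 cm² subgroup, the Randomised Set definition, the covariate-adjusted MCPMod, the analysis restricted to centres with PK-confirmed intake, analgesic consumption and ECG heart rate. None concerns volume.

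**The concern.** A secondary endpoint that the protocol defines on one scale is planned for reporting only on others. Because the SAP separates change from relative change in its own definitions and then makes an explicit exception for volume, this cannot be read as loose wording.

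Two things are at stake. First, the study report would lack the volume endpoint that the protocol names, with no recorded reason. Second, the reader would have relative reduction for area and absolute reduction for volume. The two could not be set side by side, and the volume figures would carry the spread in baseline ulcer size.

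**Working it through.** No figure in the plan needs reproducing. The check is a comparison of text, followed by a small illustration.

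**1. Is relative change in volume planned anywhere in the SAP?**

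| Place | Scale for area | Scale for volume |
|---|---|---|
| Protocol synopsis and 4.1.2 | relative | relative |
| Protocol 10.1.4, by visit | relative | not stated |
| Protocol 10.1.4, subgroups | relative | relative, on the natural reading |
| SAP 3.4.2.3 (area), 3.4.3 (volume) | raw and relative | raw and arithmetic change |
| SAP 3.4.4, subgroups | raw and relative | raw and arithmetic change |

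It is not.

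**2. Is the switch recorded?** No. The version table does record the parallel decision for linear advance, with a reason: its baseline value is zero by definition. That reason does not carry over to volume, since protocol Appendix 3 defines a venous leg ulcer as a full-thickness skin defect. The table also lists an item as small as ECG heart rate.

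**3. Can the endpoint be recovered from the planned tables?** Not from summary statistics, because the mean of individual percentages is not the percentage change in the means. Take two ulcers of 4.5 and 100 cm² at unit depth, where the first heals and the second does not change:
- mean relative reduction = (100% + 0%)/2 = 50%;
- reduction in the mean = 4.5/(4.5 + 100) = 4.3%.

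**4. How far does the scale matter?** The inputs are the inclusion limits for area, 4.5 to 100 cm² (protocol 5.3). The documents give no volume distribution, so equal depth *h* is an assumption. For a proportional reduction *r*, absolute volume change = *r* × area × *h*. At equal *r* and *h*, the ratio between the limits is 100/4.5 = 22.2. At *r* = 32.5%, for example, the reductions per unit depth are 0.325 × 4.5 = 1.46 and 0.325 × 100 = 32.5.

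**5. Could one large ulcer dominate an arm?** The SAP reports 121 included patients, so 121/6 ≈ 20 per arm. Suppose that every ulcer halves at equal depth. One 100 cm² ulcer contributes 50 units. The other 19, with mean area *m*, contribute 0.5 × 19 × *m* = 9.5*m*. The single ulcer outweighs them only if *m* < 50/9.5 = 5.3 cm².

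**The case against.** **The protocol's statistics section sets no scale for volume by visit, and the version table claims only the main changes.** Both statements are true. But a line asking for descriptive statistics does not replace the endpoint definition in 4.1.2, and the table does record the matching change for linear advance.

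**Absolute change is defensible.** Percentages are unstable when baseline volume is very small and undefined when it is zero. This is a good reason to keep absolute change and to set a rule for the denominator. It is not a reason to drop the defined endpoint without saying so. SAP 3.4.2.3 already handles a similar problem for area, by restricting the W004–W006 and W006–W008 relative changes to patients whose starting value is not zero.

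**The tables already limit the damage.** SAP 3.1.1 gives the median, quartiles, minimum and maximum. Raw volume is shown at each visit, so a baseline imbalance would be visible. Randomisation uses a size-and-age factor with a 10 cm² cut, and volume is described in subgroups cut at 10 (combined with ulcer age), 20 and 50 cm². These protections are real but partial. The 10 cm² cut does not separate an 11 cm² ulcer from a 100 cm² one, and subgroups under 20 patients get listings only. The median does not restore the relative scale either: if every ulcer halves, the median absolute change is half the median baseline volume, whatever that is in the arm.

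**Stronger readings that the documents do not support.** A reader might infer that a chance imbalance in ulcer size would pass for a dose effect. Neither document attaches a test, model or decision rule to volume; MCPMod and the minimal effective dose use area only. A reader might also infer that one large ulcer would typically swamp an arm. Step 5 shows that this needs the other 19 to average below about 5.3 cm², close to the entry floor, and nothing in the documents suggests that.

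**Conclusion.** The inconsistency is confirmed. As the SAP is written, the protocol-defined volume endpoint is not reported, the volume results are on a different scale from the area endpoint, and the departure is not recorded.

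The consequence is confined to one descriptive secondary endpoint. The primary analysis, the dose-response conclusion and the type I error rate are untouched. The endpoint is not lost, because volume is measured centrally at each visit and percentages can be derived without new data. The 22-fold figure is a ratio of area limits under assumed equal depth. It shows that the two scales are not interchangeable, and it does not estimate any bias in this trial.

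The conclusion rests on the protocol and SAP text alone. The table templates are in a separate document that was not available; if they already include relative change in volume, only the SAP wording and the version table need correcting.

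**What to change.** - In SAP 3.4.3 and 3.4.4, add relative change in volume from baseline to each visit, using the 3.1.2 definition, for patients with non-zero baseline volume. State the number excluded in each arm.
- Say that this summary is read mainly through the median and quartiles, because percentages are unstable for very shallow ulcers.
- Keep arithmetic change as supportive.
- Add an entry on the handling of volume to the version table. If the sponsor prefers to drop relative change, that entry must say so and give the reason.

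The cost is some SAP wording and one more summary per volume table. No new data, test or multiplicity adjustment is needed. The drawback is that a few extreme percentages may appear, which the median reading and the stated exclusions address.
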